6.2 Blinding and unblinding

The clinical surgeons, outcome assessors, data recorders, and statisticians will all operate independently. Due to the nature of the surgical interventions, the surgeons will not be blinded to treatment allocation. However, the outcomes assessor who assess or analyze the end point will be blinded. The patients will also be blinded to group allocation to reduce the risk of bias. Unblinding will not be performed unless the finalization of the main data analysis or required for patient's safety. After the data analysis, we will have a blinded interpretation of the study results to minimize misleading data interpretation.

7. Intervention and study flow

7.1 Preparation procedures

Prior to the surgical intervention, patients are required to undergo a series of preparation steps to ensure optimal conditions for surgery and to minimize the risk of complications. On the evening before the operation, patients will consume a solution containing polyethylene glycol electrolytes to cleanse the bowel. This bowel preparation is crucial for visualization during surgery and to reduce the risk of infection. The day before surgery, patients will also be administered oral antibiotics, specifically metronidazole at a dosage of 800 mg and gentamycin sulfate at 160 mg, to target a broad spectrum of potential infectious agents. Furthermore, as a prophylactic measure against infection, mezlocillin sodium will be given 20 minutes prior to the induction of anesthesia.

7.2 Surgical Techniques:

General Surgical Procedures: On the day of surgery, patients are positioned supine on the operating table with their legs spread to allow ample space for the surgical team. The surgeon and assistant will be positioned on the right side of the operating bed, facilitating access to the surgical site. The initial incision, approximately 10mm in size, will be made above the umbilicus using an open technique, which allows for the introduction of the primary port for laparoscopic instruments. Subsequently, four additional ports will be strategically placed under laparoscopic guidance. Throughout the procedure, the principles of complete mesocolic excision (CME) and central vascular ligation will be adhered to. This involves a medial-to-

lateral approach, where mesenteric vessels, including the inferior mesenteric vein, left colic artery, and one to two sigmoid arteries, are carefully exposed and divided at their origins using either absorbable or non-absorbable clips. The greater omentum is then separated from the transverse colon using a harmonic scalpel, and the splenic flexure and descending colon are mobilized.

7.2.1 Experimental Group Procedure

In the experimental group, the surgeon will use a 10-cm medical suture and methylene blue solution to mark the resection margin. The marginal vessels and mesentery will be divided inside the body. The proximal and distal colons are resected using a 60mm linear laparoscopic stapler. Side-to-side intracorporeal anastomotic techniques like anti-peristaltic, iso-peristaltic, or overlap methods will be applied (Figure 2-4). Once the anastomosis is completed, the specimen is retrieved. The surgeon can place the specimen in a sterile plastic bag for retrieval. Alternatively, the surgeon can use a disposable incision retraction fixator to protect the wound. An abdominal drainage tube is inserted. Three different intracorporeal anastomotic methods are shown in Figures 2, 3, and 4.

Note that only these three anastomotic methods are allowed in intracorporeal anastomosis. If the anastomosis was completed by inserting the circular stapler through the anus after patients were assigned to the IA group, it is considered a conversion to EA. This is because the surgeons had to make an incision and insert the circular stapler anvil into the proximal colon with the abdomen open. In these cases, the anastomosis was not completed under laparoscopy.

7.2.1.1 Isoperistaltic Side-to-Side Anastomosis: This method involves making two small enterotomies on the antimesenteric borders, approximately 8 cm from the ends of the colon. The colonic ends are then positioned in the upper left abdomen. Each end of a 60mm linear laparoscopic stapler is inserted through the enterotomies, closed along the antimesenteric borders, and fired to create the anastomosis (Figure 2A). Subsequently, the common enterotomy is continuously sutured using a 3-0 knotless absorbable suture (Figure 2B).

[figure not shown]

Fig. 2 A Two ends of a 60-mm linear laparoscopic stapler are inserted into the colons through enterotomies separately, then close along the antimesenteric borders and fire. B The common enterotomy is sutured continuously.

7.2.1.2 Antiperistaltic Side-to-Side Anastomosis: Similar to the isoperistaltic method, two small enterotomies are made on the antimesenteric borders of the colon ends. These ends are placed near the midline of the abdomen. The 60mm linear laparoscopic stapler is used in the same manner to close the antimesenteric borders and create the anastomosis (Figure 3A). The common enterotomy can then be closed using either a reloaded 60mm linear laparoscopic stapler positioned perpendicular to the colon ends (Figure 3B) or by continuous suturing with a 3-0 knotless absorbable suture.

[figure not shown]

Fig. 3 A Two ends of 60-mm linear laparoscopic stapler are inserted into the colons through enterotomies separately, then close along the antimesenteric borders and fire. B The common enterotomy is closed by a reload 60-mm linear laparoscopic stapler perpendicular to colon ends

7.2.1.3 Overlap Side-to-Side Anastomosis: The choice between a cephalic or caudal

approach for inserting the linear laparoscopic stapler depends on the tumor location and the ease of anastomosis. When the transverse colon end has limited mobility, the caudal approach offers greater convenience (Figure 4A). In this approach, one small enterotomy is made at the antimesenteric border of the transverse colon end, and another enterotomy is made approximately 8 cm from the descending or sigmoid colon end. The 60 mm linear laparoscopic stapler is inserted through the caudal trocars, with both ends being introduced into the colons via the enterotomies, closed along the antimesenteric borders, and fired to complete the anastomosis (Figure 4B). The common enterotomy is then continuously sutured using a 3-0 knotless absorbable suture. In the cephalic approach, the positions of the two enterotomies on the colons are made in opposition to those in the caudal cases.

[figure not shown]

Fig. 4 A Two ends of 60-mm linear laparoscopic stapler are inserted into the colons through the enterotomies separately, then close along the antimesenteric borders and fire. B The common enterotomy is sutured continuously

7.2.2 Control Group Procedures:

For patients in the control group, the surgeon uses wound edge protectors to exteriorize the colon through a small incision in the midline of the abdomen. A ruler and methylene blue solution are employed to mark the area for colon resection. This guarantees a 10-cm margin from the tumor. Guided by these markers, the marginal vessels and mesentery are divided outside the body. The method of anastomosis is at the surgeon's discretion. A side-to-side anastomosis (including antiperistaltic, isoperistaltic, or overlapping anastomosis) is recommended. Side-to-end or end-to-end anastomosis (sewn by hand or by inserting a circular stapler through the anus or proximal colon) is also allowed (Figure 5). After completing the

anastomosis, the incision is sutured. An abdominal drainage tube is inserted at the end of the operation.

[figure not shown]

Fig. 5 A Side-to-end anastomosis. It can be completed by inserting a circular stapler through the anus. Alternatively, it can be done by inserting the circular stapler through the end of the proximal colon and then using another linear stapler to close the end of the proximal colon after anastomosis. Hand sewing is also permitted. B end-to-end anastomosis. It can be completed by inserting a circular stapler through the anus. Alternatively, it can be done by sewing it by hand.

Table 1 The time point and assessments of the STARS study

Time point	Study period		Follow-up (month)					
	Screening	Treatment	1	12	24	36	48	60
Informed consent	✓							
Inclusion criteria	✓							
Exclusion criteria	✓	✓	✓	✓	✓	✓	✓	✓
Baseline data	✓							
Blood test	✓							
Tumor marker test	✓							
Chest CT	✓							
Pelvic MRI	✓							
Abdominal CT	✓		✓					
Electrocardiogram	✓							
Colonoscopy	✓							
Surgery		✓						
Complications		✓	✓					
Recurrence/death			✓	✓	✓	✓	✓	✓

7.3 Concurrent treatment and follow-up.

Postoperative chemotherapy is recommended according to the NCCN guidelines for colon

cancer treatment. The post-operative follow-up period must be in accordance with the time specified in this study (Table 1). Each participant will be followed until recurrence or death over a period of 5 years after the scheduled surgery.

The follow-up period for the primary endpoint is within 30 days after surgery. Follow-up will be conducted through in-patient observation, outpatient consultations, and telephone inquiries. SSI presence will be assessed daily during hospitalization and weekly after discharge. At least two surgeons perform SSI surveillance. The outcome assessors are trained on the Centers for Disease Control and Prevention (CDC) definitions of SSI to produce good inter-rater reliability for the assessment of SSI. If SSI is suspected during follow-up, CT or abdominal ultrasonography will be done. All patients will have an abdominal or pelvic CT on the 30th day after surgery. If the CT shows evidence of SSI, the radiologist and surgeon will assess whether there is an SSI.

The patient's surgery-related complications and Clavien–Dindo grade within 30 postoperative days will be recorded. The overall follow-up period for patients after surgery is 5 years, which includes 5-year overall survival (OS) and 3-year disease-free survival (DFS). For patients with recurrent tumors, follow-up should continue for at least 3 years after recurrence or metastasis is discovered or until death.

Appropriate strategies will be used to improve patient adherence and ensure data integrity. When signing the informed consent form, all participants will be informed of the study procedures, potential benefits, and risks to make them fully understand the inconvenience and significance of data collection.

In addition, patients who have had abdominal surgery need to return to our hospital for other treatment of combined injuries, including suture removal. Our medical team will provide standard post-operative care for enrolled participants to promote their adherence.

Investigators will contact patients 1 week before the follow-up session to increase the attendance rate. Patients who miss a scheduled appointment will be contacted to reschedule another appointment within 1 week. Telephone follow-up calls, WeChat group discussions, and personal interviews will be used to maximize retention and complete follow-up.

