(8) Length of incision: The incision length is measured with an aseptic ruler at the end of the surgery, after the incision is sutured. It is measured in millimeters.

(9) Visual analog score (VAS) of pain: Pain severity was assessed 48 hours after the operation using a ruler about 10 cm long. The ruler is numbered from 0 to 10. 0–3 points indicate no to mild pain. 4–6 points represent moderate pain. 7–10 points stand for severe pain.

(10) 3-year disease-free survival (DFS) and 5-year overall survival (OS): DFS was defined as the time from randomization until the discovery of local recurrence, distant metastasis, or

death from the tumor. OS was defined as the time from randomization to death due to any cause.

4. Study design

[figure not shown]

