12.3.2 Secondary endpoint analysis

The analysis of the secondary endpoints will be carried out in the mITT population. In the analysis of secondary endpoints, categorical variables will be reported as frequencies and percentages. Groups will be compared using the χ^2 test or Fisher's exact test. Absolute risk differences and the corresponding 95% CI will be calculated. Continuous variables will be described as mean \pm standard deviation or median (quartile). Groups will be compared using the t-test or Mann-Whitney U test, as appropriate. Hodges-Lehmann method will be used to calculate the difference in median and the corresponding 95% CI.

The comparison of 3-year DFS and 3-year OS between the two groups will utilize the Kaplan-Meier curve and the Cox proportional risk model. Relevant risk factors will be adjusted in Cox proportional risk model.

The missing data in this trial is expected to be minimal. If it occurs, it will be treated as censored data and not imputed. All statistical tests were 2-sided, and statistical significance was set at $P < 0.05$. All statistical analyses were performed using R or SPSS.

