14.2 Patients information and informed consent

Eligible patients should receive in-person notification from the treating surgeon and written information about the trial. Each patient should provide informed consent in accordance with local ethics committee guidelines before entering the random allocation of studies.

The informed consent procedure should be carried out by the doctors of each centre. Information provided to patients with informed consent includes: 1) a statement about the study involved in the trial; 2) a full and fair explanation of the procedures to be followed; 3) a full explanation of the nature, anticipated length, and purpose of the study; 4) a description of any risk or discomfort that the patient can reasonably anticipate; 5) a description of any benefits that can be reasonably anticipated; 6) a statement that patient data will be treated with care and confidentiality and that the data will be kept for 15 years; 7) a statement about the patient's physical material will be kept for 15 years; 8) a statement about voluntary participation, where

the statement will state the refusal Participation in the trial does not involve any punishment or loss of benefits the patient is entitled to, and patients can stop participating at any time without being penalized or losing benefits, in which case the patient will receive standard treatment with the same level of care.

15. Definition of Study Completion

The completion of the study was defined as all enrolled patients completed 5 years of follow-up. Follow-up outcomes include disease-free survival, recurrence survival, death, or loss of visits.

16. Study organizational structure

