4.1 General calculation rules

All statistical tests were 2-sided, and statistical significance was set at $P < 0.05$. All statistical analyses were performed using R or SPSS. P-values will be quoted to three decimal places. Confidence intervals (CI) will be two-sided and 95%. CI will also be quoted to one decimal place.

Categorical variables will be reported as frequencies and percentages. Percentages will be quoted to one decimal place. Chi-square tests in contingency tables will be replaced by Fisher's exact tests if any expected cell frequency is less than five.

Absolute risk differences and the corresponding 95% CI will be calculated.

Continuous data with normal distribution were presented as mean (standard deviation) and analyzed by Student's t-test. Continuous variables with non-normal distribution were reported as medians (quartile) and compared using the Mann-Whitney U test. Hodges-Lehmann method will be used to calculate the difference in median and the corresponding 95% CI. Data will be quoted to one decimal place.

Survival data between two groups will be compared using a two-sided log-rank test stratified by pathological TNM (0–I, II, III) and age (≤ 65 years and > 65 years). The hazard ratio (HR) for disease recurrence or death will be estimated using the stratified Cox proportional hazards model, including strata of pathological TNM (0–I, II, III) and age (≤ 65 years and > 65 years). The 95% confidence interval for the HR will be constructed. Results from an unstratified analysis will also be provided. The Kaplan-

Meier methodology will be applied to estimate the median disease-free survival (DFS) and overall survival (OS) for each treatment arm. Kaplan-Meier curves will be developed.

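### Protocol v2.1 specifies overall survival inconsistently: section 7.3 contradicts itself on follow-up after recurrence, and section 12.3.2 compares 3-year OS although the endpoint is 5-year OS

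*Combined protocol and SAP*

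**What the plan says.** **Follow-up.** Section 7.3 of protocol v2.1 first ties postoperative follow-up to Table 1, which ticks recurrence/death at months 1, 12, 24, 36, 48 and 60. The next sentence reads "Each participant will be followed until recurrence or death over a period of 5 years after the scheduled surgery". Later in the same section, "The overall follow-up period for patients after surgery is 5 years", which is said to include 5-year OS and 3-year DFS. This is followed at once by "For patients with recurrent tumors, follow-up should continue for at least 3 years after recurrence or metastasis is discovered or until death". The v2.1 abstract repeats the last rule. Section 15 also rests on five years: "The completion of the study was defined as all enrolled patients completed 5 years of" follow-up.

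**Time point.** Section 3.2.2 (10) names the endpoints as "3-year disease-free survival (DFS) and 5-year overall survival (OS"), with OS running from randomization to death from any cause. SAP 4.6 also names 5-year OS. Section 12.3.2 of the protocol instead plans "The comparison of 3-year DFS and 3-year OS between the two groups".

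**Estimate.** SAP 4.1 uses Kaplan-Meier to "estimate the median disease-free survival (DFS) and overall survival (OS) for each treatment arm". It also plans a stratified log-rank test, stratified and unstratified Cox hazard ratios, and Kaplan-Meier curves. Neither document explicitly plans a Kaplan-Meier estimate of DFS at 36 months or OS at 60 months with a confidence interval.

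**The concern.** OS needs vital status after recurrence, because many cancer deaths come after it. A rule that ends follow-up at recurrence removes those deaths and censors the patients most likely to die, so the censoring is informative. The SAP gives no protection here: its OS censoring rule covers patients lost to follow-up, not patients whose follow-up ended by rule. The abstract lists twelve centres, and each could act on either sentence in 7.3. Deaths that were not collected may not be recoverable when survival is analysed.

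Separately, a 3-year OS comparison is not the endpoint that the protocol and SAP define. A median may also not be estimable, in which case the SAP names no numerical survival estimate per arm that matches the named endpoints.

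**Working it through.** **1. The plan's own figure.** The only sample-size figure is for SSI (13.3% EA, 8.0% IA, margin 5%, one-sided 0.025, power 0.80, 20% drop-out).

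n per arm = [0.133×0.867 + 0.080×0.920] × (1.960 + 0.842)² / (0.05 + 0.133 − 0.080)² = 139.8, rounded up to 140. Then 140/0.80 = 175 per arm, 350 in total, as stated. No OS rate, hazard ratio, event count or power is given, so nothing in this point changes the 350.

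**2. The follow-up rules side by side.**

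| Recurrence at | Until recurrence or death | Exactly 3 years after recurrence | 5 years for all / Table 1 |
|---|---|---|---|
| month 12 | stop at 12 | stop at 48 | to 60 |
| month 24 | stop at 24 | stop at 60 | to 60 |
| month 40 | stop at 40 | stop at 76 | to 60 |

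The first column is incompatible with the other two. The second falls short of month 60 only for recurrence before month 24, and only if the 3-year minimum is read as a stopping point.

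**3. Size if a site stopped at recurrence.** All survival inputs are assumptions, since the documents give none: recurrence R = 20% or 25% by month 60, median survival after recurrence m = 24 or 36 months, other-cause death 5% by month 60, constant hazards.

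- h = −ln(1−R)/60; o = −ln(0.95)/60 = 0.000855; λ = ln 2/m.
- True OS: S(60) = e^(−60o) × {e^(−60h) + [h/(λ−h)] × [e^(−60h) − e^(−60λ)]}.
- Deaths before recurrence: D0 = [o/(o+h)] × [1 − e^(−60(o+h))].
- Share of deaths missed = 1 − D0/(1 − S(60)).
- Kaplan-Meier OS with censoring at recurrence: e^(−60o) = 0.95 in every scenario.

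Example, R = 20%, m = 24: h = 0.003719 and λ = 0.028881, so S(60) = 0.95 × {0.800 + 0.1478 × (0.800 − 0.177)} = 0.847. D0 = 0.0449, and the share missed is 1 − 0.0449/0.1525 = 71%.

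For deaths missed when follow-up stops exactly 3 years after recurrence, integrate over recurrence times t from 0 to 24: h e^(−(h+o)t) × [e^(−36(λ+o)) − e^(−(λ+o)(60−t))].

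| R, m | True 5-year OS | Reads as | Deaths per 350 | Missed, stop at recurrence | Missed, stop 3 years later |
|---|---|---|---|---|---|
| 20%, 24 | 84.7% | 95% | 53 | 38 (71%) | 2.9 |
| 20%, 36 | 87.0% | 95% | 45 | 30 (65%) | 3.0 |
| 25%, 24 | 82.1% | 95% | 63 | 48 (76%) | 3.8 |
| 25%, 36 | 84.9% | 95% | 53 | 37 (71%) | 3.9 |

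A wider set of assumptions (3-year recurrence-free proportion 75–85%, post-recurrence median 18–36 months, other-cause mortality 1–2% a year) gives 55–86% of deaths missed, and 3–6 per 350 under the 3-year stop.

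**4. 3-year against 5-year OS.** Under exponential survival in 350 patients, assumed 5-year OS of 70/80/90% gives 67/44/21 deaths by year 3 and 105/70/35 by year 5. An analysis cut at year 3 would use 60–64% of the deaths.

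**5. The median.** It is reached by month 60 only if 5-year OS is 50% or lower. Even if the earliest patients were followed to month 96 (3 years of recruitment plus 5), exponential survival would need 5-year OS of at most 0.5^(60/96) = 65%.

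**The case against.** The strongest reply is that one loose sentence should not be taken as the operative rule. The sentence before it defers to Table 1, which runs to month 60. The abstract and the later part of 7.3 continue follow-up after recurrence. Sections 4.2, 12.5 and 15 and SAP section 7 all rest on five years in every patient. This stands. A reader might infer that the plan ends OS follow-up at recurrence, but the documents do not support that. They contradict themselves, and the weight of the text is on the side of five years.

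The 3-year rule is worded as a minimum and directly follows the 5-year sentence, so reading it as permission to stop at month 48 is strained. This also stands, and even on that reading the loss is small. What remains is that no sentence says outright that vital status is collected to month 60 regardless of recurrence.

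A reader might also infer that DFS is biased. It is not: recurrence is a DFS event, so stopping there loses nothing for DFS. Nor does the calculation show bias in the IA–EA comparison, since it describes a single arm.

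On the time point, the later SAP, written from protocol v2.1, uses 5-year OS, and Kaplan-Meier and Cox methods use all follow-up time. The conflict is therefore confined to 12.3.2, but it is real. On the median, the log-rank test, hazard ratios and curves do not need one, so it would be too strong to say that survival would go unreported.

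**Conclusion.** The point holds as an internal inconsistency in how OS is specified. Two conflicts need no assumption: the two follow-up rules in 7.3, and 3-year against 5-year OS. The missing fixed-time estimates are likewise a matter of reading the text.

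The size is conditional on a site applying the first sentence of the conflict literally. Then a true 5-year OS of 82–87% would read about 95%, with 65–76% of deaths missed. Under a stop exactly 3 years after recurrence, about 3–4 deaths per 350 would be missed. These figures rest on assumed recurrence and survival rates and constant hazards. That the medians will not be reached is plausible in M0 disease but is also an assumption.

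It would go too far to conclude that the survival endpoints are undermined. OS is a secondary endpoint with no stated power. The primary 30-day SSI endpoint and the sample size of 350 are untouched.

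**What to change.** - **Protocol 7.3:** reconcile the follow-up sentences so that vital status is collected for every participant to death or month 60, whether or not the tumour recurs. State how the 3-year rule after recurrence relates to month 60.
- **Protocol 12.3.2:** change 3-year OS to 5-year OS, to agree with 3.2.2 and SAP 4.6.
- **SAP 4.1:** add Kaplan-Meier estimates of DFS at 36 months and OS at 60 months by arm, with 95% confidence intervals. Report medians only if reached.

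The cost is wording in the protocol and SAP. Table 1 already schedules recurrence/death checks to month 60, so no visits are added. The 7.3 edit should come first, because missing follow-up is harder to repair later than an analysis specification.

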4.2 Study time frame

The subject recruitment period is 3 years, and the follow-up period lasts 5 years. The entire study, which includes study establishment, patient recruitment, patient follow-up, and data analysis, is expected to take 8 years. We'll conduct a primary endpoint analysis of the study after all patients finish their first month of post-operative follow-up. Additionally, a second analysis of results involving survival data will be done after all patients complete 5 years of follow-up.

Figure 1 the study design flowchart

5. Study population

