4.6 Secondary endpoints

The secondary endpoints will be compared between groups in the mITT population, PP population, and AT population.

- Operating time, continuous variable, measured in minutes;
- Total blood loss during operation, continuous variable, measured in milliliters;
- Conversion to open surgery, categorical variable;
- Postoperative complications, categorical variable. It will be analyzed according to the overall occurrence. The occurrence of its subtype (anastomotic leakage, bowel obstruction, etc.) will also be analyzed. Additionally, Clavien–Dindo classification will be analyzed (\leq grade II, \geq grade III). (3)
- Completeness of specimens, categorical variable. It is evaluated according to the West classification (mesocolic plane, intramesocolic plane, and muscularis propria plane).(4)
- Number of lymph nodes dissected, continuous variable.
- The pathological TNM stage (as per the American Joint Committee on Cancer

Cancer Staging Manual, 8th edition), categorical variable. The T stage, N stage, and TNM stage will be analyzed separately.

- Postoperative recovery, continuous variable. It includes the time to first flatus, the time to first defecation, the time to start food intake, and the postoperative hospital stay. Additionally, the time to first ambulation and the time to remove the abdominal drainage tube, which are not included in the study protocol's design, will also be analyzed. These are measured in days.
- Length of incision, continuous variable. It is measured in millimeters.
- Visual analog score (VAS) of pain, it will be analyzed as categorical variable: no to mild pain (0–3 points); moderate pain (4–6 points), and severe pain (7–10 points).
- 3-year DFS: DFS is defined as the time from randomization until the occurrence of local recurrence, distant metastasis, or death from the tumor, whichever comes first. It is measured in months. For patients who are lost to follow-up, DFS will be censored at the time of the last available tumor assessment before the missing assessments.
- 5-year OS: OS was defined as the time from randomization to death due to any cause. It is measured in months. For patients lost to follow-up, OS will be censored at the time of the last available follow-up prior to the missing assessments.

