4.7 Subgroup analysis

The subgroup analysis will be carried out only if the primary endpoint in the mITT population do not reach the non-inferiority margin. If the 95% CI of SSI is not within the non-inferiority margin, the primary endpoint will be summarized within the following subgroups.

- Sex (male, female);
- Age (≤ 65 years, > 65 years);
- Body Mass Index ($\leq 24 \text{ kg/m}^2$, $> 24 \text{ kg/m}^2$);
- Tumor site (distal transverse colon or splenic flexure of colon, descending colon,

proximal sigmoid colon);

- NRS2002 score (≤ 2 points, > 2 points);
- Mechanical bowel preparation (Yes, No);
- Oral antibiotic bowel preparation (Yes, No);
- Postoperative antibiotic use time(≥ 3 days, < 3 days);
- Operating time (≤ 180 mins, > 180 mins);

Subgroup analyses will be performed using mITT population. If intracorporeal anastomosis is proven to be noninferior to extracorporeal anastomosis regarding SSI, subgroup analysis will not be performed.

5 Missing data

Missing primary endpoint data will be treated as censored data and won't be imputed during analysis. Other missing data won't be imputed either. The missing data will be stated in the tables.

6 Interim analyses

No interim analyses are planned in this study.

7 Timing of analysis

We will conduct an analysis of the study's primary endpoint and publish the relevant findings after enrollment is completed and all patients have completed the first month of follow-up after surgery. When all patients complete 5 years of follow-up, the results involving survival data will be analyzed again, and the relevant research results will be published.

Reference

1. He L, Li M, Zhang J xin, Tong W hua, Chen Y, Wang Q. Surgical site infection after intracorporeal anastomosis for left-sided colon cancer: study protocol for a non-

inferiority multicenter randomized controlled trial (STARS). *Trials*. 2022 Nov 22;23(1):954.

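### OS has no 60-month censoring rule although only recurrent patients are followed longer, so the curve after month 60 and any median read from it can be spurious; 5-year OS is unaffected

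*Combined protocol and SAP*

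**What the plan says.** - **Follow-up of all patients.** Protocol v2.1, 7.3: "The overall follow-up period for patients after surgery is 5 years". The recurrence/death row of Table 1 ends at month 60.
- **Follow-up of recurrent patients.** Same section, and also the abstract: "For patients with recurrent tumors, follow-up should continue for at least 3 years after recurrence or metastasis is discovered or until death".
- **A conflicting sentence, also in 7.3.** "Each participant will be followed until recurrence or death over a period of 5 years after the scheduled surgery".
- **Calendar.** Protocol v2.1, 4.2: "The subject recruitment period is 3 years, and the follow-up period lasts 5 years". SAP 7: "When all patients complete 5 years of follow-up, the results involving survival data will be analyzed again".
- **OS analysis.** SAP 4.1 plans a stratified log-rank test, a stratified Cox model and Kaplan–Meier curves, and the Kaplan–"Meier methodology will be applied to estimate the median disease-free survival (DFS) and overall survival (OS) for each treatment arm".
- **OS censoring.** SAP 4.6 labels the endpoint 5-year OS and defines it as time from randomisation to death from any cause. Its one censoring rule is: "For patients lost to follow-up, OS will be censored at the time of the last available follow-up prior to the missing assessments".
- **Horizon.** Protocol v2.1, 3.2.2 (10) and SAP 4.6 name 5-year OS. Protocol v2.1, 12.3.2 compares 3-year OS.

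**The concern.** Kaplan–Meier, log-rank and Cox methods assume that patients who leave observation have the same prognosis as those who stay. After month 60 the follow-up rule breaks this by design. Recurrence-free survivors stop at month 60, while patients with a later recurrence stay under observation. Recurrence strongly predicts death, so the late risk set has a far higher death rate than the cohort it is meant to represent.

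The SAP requests two outputs that use this stretch of the curve: the plotted OS curve and the median OS per arm. Without a cut-off, a trial in which most patients are alive at 7 years could publish a curve dropping through 50% and quote a median OS that does not exist.

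**Working it through.** **The plan's own figure.** The only computed design figure is the sample size, and it concerns SSI. With rates of 13.3% and 8.0%, a 5% margin, one-sided 0.025 and 80% power, n = (1.960 + 0.842)² × (0.133×0.867 + 0.080×0.920) / (0.05 + 0.053)² = 7.85 × 0.1889 / 0.01061 ≈ 140 per arm. Then 140/0.80 = 175 per arm, 350 in total, as stated. No OS event count, effect size or power is given, so this supplies only the number of patients.

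**Who is observed after month 60.**
- Recurrence at month r gives follow-up to at least r + 36, which passes 60 when r > 24.
- Recurrence-free patients stop at 60.
- Survival is analysed when the last patient reaches 60 months. With 36 months of accrual, the first patients are then 36 + 60 = 96 months from entry, so extended follow-up of early enrollees can be in the data.

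**Assumptions.** Reference 5-year recurrence 15–35%, median survival after recurrence 24–36 months, other-cause death 0.5–1.5% per year, recurrence hazard ratio 1.0 or 0.7, uniform accrual, no loss to follow-up, 350 patients, 1,500 simulated trials per scenario. OS of both arms pooled:

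| Recurrence, median after it, other-cause/yr, recurrence HR | Month 60 | 72 / 84 as planned | 72 / 84, everyone followed | Median reached: planned / everyone followed |
|---|---|---|---|---|
| 15%, 24 mo, 1%, 1 | 0.875 | 0.613 / 0.441 | 0.842 / 0.810 | 67.7% / 0.1% |
| 25%, 24 mo, 1%, 1 | 0.822 | 0.574 / 0.408 | 0.776 / 0.731 | 80.3% / 0.5% |
| 25%, 36 mo, 1%, 1 | 0.851 | 0.669 / 0.531 | 0.810 / 0.769 | 48.8% / 0.2% |
| 25%, 36 mo, 1%, 0.7 | 0.863 | 0.679 / 0.541 | 0.827 / 0.790 | 45.1% / 0.0% |
| 25%, 24 mo, 1%, 0.7 | 0.840 | 0.584 / 0.412 | 0.799 / 0.758 | 76.5% / 0.4% |
| 15%, 36 mo, 0.5%, 0.7 | 0.923 | 0.729 / 0.583 | 0.901 / 0.878 | 36.1% / 0.0% |
| 35%, 24 mo, 1.5%, 0.7 | 0.772 | 0.539 / 0.371 | 0.717 / 0.663 | 89.7% / 2.5% |

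The month-60 value is the same under both follow-up rules.

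**Hand check.** With only recurrent patients at risk, the curve after month 60 is S(60) × 0.5^((t−60)/m) × (1−c)^((t−60)/12), where m is the median survival after recurrence and c the yearly other-cause death rate. In the second row at month 72 this is 0.822 × 0.5^(12/24) × 0.99 = 0.822 × 0.707 × 0.99 = 0.575 (simulated 0.574). At month 84 it is 0.822 × 0.5 × 0.980 = 0.403 (simulated 0.408).

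**Per arm.** A second set of assumptions used 140 per arm, 3-year recurrence-free 75–85% and median survival after recurrence 18–30 months. With 80% and 30 months, OS was 0.81 at month 60, then about 0.60 and 0.45 at 72 and 84, against true values of about 0.76 and 0.73. A median was reached in 53–93% of arms over the range.

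**Size of the tail.** 18 to 34 of 350 patients remain after month 60 in the first set (9 to 17 per arm) and 12 to 18 per arm in the second. In the second set's base case about 15 per arm remain after month 60, 6 at month 72 and 1 at month 84.

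**Deaths after month 60.** From 30.8 − 26.9 = 3.9 to 90.0 − 79.8 = 10.2 of 350 patients, or 11–13% of all observed deaths.

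**Hazard ratio.** With equal arms the planned analysis gives 0.99–1.01, as does the 60-month cut. With a recurrence hazard ratio of 0.7 it gives 0.80–0.82, against 0.78–0.80 with the cut and 0.77–0.79 with everyone followed. The largest shift, 0.798 against 0.775, is ln(0.798/0.775) = 0.029. With 63.8 deaths the standard error is about 2/√63.8 = 0.25, so the shift is about 0.12 standard errors. In the second set, a 1.5-fold recurrence increase gave 1.30 planned against 1.35 with the cut: 0.038 on the log scale, or about 0.15 standard errors with roughly 60 deaths.

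**The case against.** Every OS horizon the documents name, 3 or 5 years, lies at or before month 60, and Table 1 has no later visit. Protocol 7.3 also says that each participant is followed until recurrence or death within 5 years. On that sentence nobody is observed past month 60 and the problem does not arise. The tail rests on very few patients, every survival rate is assumed, and OS is part of the last of ten secondary endpoints with no stated power.

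Much of this stands. It limits the point to a conditional one: the distortion occurs if the extended follow-up enters the analysis. It does not remove it. A 5-year label is not a censoring rule, and the SAP asks for a median and a hazard ratio without restricting time. The conflicting sentence is no defence either, since stopping follow-up at recurrence would itself censor OS informatively.

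A reader might infer that 5-year OS is biased, that the whole OS curve and Cox model rest on recurrent patients only, or that the comparison of the arms is unsound. The documents do not support this. Everyone is followed to month 60, so the curve to that point is unaffected. About 88% of deaths enter the Cox model from ordinary risk sets, and the shift in the hazard ratio is far below its standard error.

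**Conclusion.** Wrong as written, but minor. As the plan stands, observation after month 60 depends on recurrence, and no SAP rule keeps that period out of the OS analysis. Under the assumed rates, OS at month 84 would read 0.37–0.58 where 0.66–0.88 is correct. A median OS would be reached in about 50–90% of arms (36–90% of trials for the pooled curve), although with everyone followed the pooled curve reaches one in at most 2.5% of trials. The harm is confined to the curve after month 60 and the median. The hazard ratio moves by about 0.02–0.05 towards 1 when the arms differ and not at all when they are equal. OS to month 60 is untouched, and the SSI primary analysis is not involved. The direction follows from the follow-up rule; the sizes depend on the assumed rates and on no loss to follow-up.

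**What to change.** Before the survival data are analysed:

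1. In SAP 4.1 and 4.6, censor OS administratively at 60 months from randomisation for every patient in the Kaplan–Meier, log-rank and Cox analyses.
2. Report median OS as not reached if the curve is still above 50% at 60 months.
3. Report later follow-up of recurrent patients separately, as post-recurrence survival measured from the date of recurrence.
4. In protocol 7.3, reconcile the sentence that ends follow-up at recurrence with the one that extends it.
5. Reconcile the 3-year OS in protocol 12.3.2 with the 5-year OS in protocol 3.2.2 and SAP 4.6.

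Items 1 to 3 take a few lines in the SAP and no new data. The price is that about 12% of observed deaths leave the OS model. In the example with 63.8 deaths, 56.0 remain and the standard error of the log hazard ratio rises by a factor of √(63.8/56.0) = 1.07. Those deaths lie outside the endpoint as labelled. Collecting survival status on all patients to a common data cut-off would also remove the problem and keep the late deaths, but it needs follow-up that the protocol does not provide for.
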